2.1. Study Rationale

Based on the high frequency of synovitis in hand OA, especially in erosive disease (1), and the relationships to pain (2, 3), there is a significant rationale for testing MTX in the management of the phenotype inflammatory erosive hand OA. The updated international guidelines for management of hand OA recently concluded that future well-designed larger RCTs are needed to explore the efficacy of MTX (4), and more knowledge is needed regarding how to optimize personalized treatment in OA. A recent double-blind, randomized, placebo-controlled trial (the METHODS study) involving participants with hand OA and synovitis treated with 20 mg MTX weekly for 6 months resulted in a significant reduction in pain compared to placebo (mean between-group difference of -9.9 mm on a 100 mm visual analogue scale, 95% CI -19.3 to -0.6, p=0.037) (5). However, although the study was designed to find out whether MTX reduced pain and radiographic progression in 2 years, the COVID-19 pandemic and subsequent lockdowns in Australia altered the trial protocol, focusing on pain reduction at 6 months as the primary endpoint, and no imaging results have been published.

Participants in the ongoing MERINO trial are randomized to placebo or MTX for one year. The study encompasses extensive data collection including radiographs, ultrasound, MRI, clinical examination, laboratory tests, and a large range of patient-reported outcomes. Several participants in the MERINO trial ask if they can receive MTX after MERINO. Although not evidence-based, MTX is occasionally used off-label in erosive hand OA patients with unmanageable pain and inflammation and is considered on an individual level in conjunction with the physician and participant.

In this proposed open-label observational study, the MERINO:2 study, we will do a structured follow-up of all participants after the MERINO trial, some of whom will be prescribed MTX after the MERINO trial. In addition to ordinary follow-up consultations in the outpatient clinic, we will organize electronic questionnaires and hand radiographs 30 months after entering the MERINO trial. We see this as an opportunity to re-use existing electronic data collection schemes and ongoing collaborations with our service departments to provide a structured and long-term follow-up of participants who seek to receive MTX treatment after the MERINO RCT trial.

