4.1. Overall Design

The MERINO:2 is an investigator-initiated and open label observational study with one-year parallel group treatment with MTX in male and female adults with erosive hand osteoarthritis.

Eligible participants are those recruited to the MERINO-trial (EudraCT number 2019-004641-33, Clincaltrials.gov number NCT04579848, REK ID 2020/187524, CTIS number 2023-510523-30-00).

After the MERINO trial, participants may either continue treatment as usual or be prescribed MTX open-label (oral or s.c. 5-25mg per week as well as folic acid 1mg daily).

Especially of interest is to compare those who first receive placebo and then treatment as usual throughout the MERINO and MERINO:2 trials with those receiving MTX throughout the whole period, as this comparison will reflect the effect of long-term treatment with MTX over 2,5 consecutive years. Further, the Placebo→MTX crossover group will complement the data from the MERINO trial on shorter MTX treatment.

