4.4. End-of-Study Definition

The end of the study is defined as the date of the last scheduled procedure shown in the schedule of activities for the last participant in the study.

A participant is considered to have completed the study if the participant has completed one-time follow-up procedure shown in the SoA 30 months after entering the original MERINO trial.

5. Study Population

All participants entering the MERINO trial (see section 4.1) will be asked if they can voluntarily can provide a 30-month conventional radiographs and an electronic questionnaire. This results in four potential arms of the MERINO:2 trial, depending on the two former arms of the MERINO trial (Table 2).

The participants must be capable of giving signed informed consent as described in Appendix 1 which includes compliance with the requirements and restrictions listed in the informed consent form (ICF) and in this protocol.

We otherwise refer to the MERINO-protocol for study population description.

Table 2. Study Arms

| MERINO | MERINO:2 |
|--------------------|----------------------------------|
| 12 months | 18 months |
| MTX 10-20mg weekly | \rightarrow Treatment as usual |
| MTX 10-20mg weekly | → MTX 7,5-20mg weekly |
| Placebo | \rightarrow Treatment as usual |
| Placebo | → MTX 7,5-20mg weekly |

6. Study Intervention(s) and Concomitant Therapy

Study interventions are all pre-specified, investigational, and non-investigational medicinal products intended to be administered to the study participants during the study conduct.

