6.1.1. Investigational medicinal product (IMP)

MTX 2.5 mg oral tablet; standard treatment is 15 mg x 1 per week the first two weeks, and then 20 mg x 1 per week to end of study. Physician may deviate from standard treatment dose, example in the case of adverse events, preferences by the participants or similar. Subcutaneous MTX can be provided and will be treated equally to oral tablets.

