9.1. Statistical Hypotheses

The primary objective is to demonstrate that MTX is superior to treatment as usual in achieving slower radiographic progression at 30 months. Thus, the null hypothesis to be tested in relation to the primary estimand is as follows:

• Null hypothesis: MTX treatment for 30 months is not different from placebo (12 months) and subsequent treatment as usual (18 months) with respect to the progression of Verbruggen-Veys scoring system in participants with erosive hand OA.

VS.

• Alternative hypothesis: MTX treatment for 30 months is different from placebo (12 months) and subsequent treatment as usual (18 months) with respect to the progression of Verbruggen-Veys scoring system in participants with erosive hand OA.

Secondary outcomes (1):

- Null hypothesis: MTX treatment for 30 months is not different from placebo (12 months) and subsequent treatment as usual (18 months) with respect to the progression of KL scale or OARSI atlas in participants with erosive hand OA.
- Alternative hypothesis: MTX treatment for 30 months is different from placebo (12 months) and subsequent treatment as usual (18 months) with respect to the progression of KL scale or OARSI atlas in participants with erosive hand OA.

Secondary objective (2)

- Null hypothesis: MTX is not different from placebo/treatment as usual with respect to change from baseline to 12/30 months in OMERACT-OARSI responder criteria, AUSCAN or EQ-5D-5L.
- Alternative hypothesis: MTX is different from placebo/treatment as usual with respect to change from baseline to 12/30 months in OMERACT-OARSI responder criteria, AUSCAN or EQ-5D-5L.

Multiplicity control is not relevant for the study.

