9.2. Analysis Sets

| Participant Analysis Set | Description |
|---------------------------|---|
| Full analysis set (FAS) | All randomized participants. |
| Safety analysis set (SAS) | All participants who are exposed to investigational intervention. |

For the purposes of analysis, the following analysis sets are defined:

The full analysis set will be used to analyze endpoints related to the efficacy objectives and the safety analysis set will be used to analyze the endpoints and assessments related to safety.

For the efficacy analyses, participants will be included in the analyses according to the planned investigational intervention; whereas for safety analyses, participants will be included in the analyses according to the investigational intervention they actually received.

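### Sections 9.1 and 9.2 do not match: the 30-month hypothesis compares two treatment sequences, while efficacy is grouped by an undefined planned intervention

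*Protocol*

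**What the plan says.** - **Hypothesis (9.1).** The primary null is that "MTX treatment for 30 months is not different from placebo (12 months) and subsequent treatment as usual (18 months") in progression of the Verbruggen-Veys score. The radiographic secondary outcomes use the same contrast. Secondary objective 2 is looser: it compares MTX with placebo/treatment as usual on "change from baseline to 12/30 months in OMERACT-OARSI responder criteria, AUSCAN or EQ-5D-5L".
- **Design (4.1).** The comparison singled out is placebo followed by treatment as usual against "those receiving MTX throughout the whole period, as this comparison will reflect the effect of long-term treatment with MTX over 2,5 consecutive years".
- **Grouping (9.2).** Efficacy uses the full analysis set, defined as everyone randomised, with this rule: "For the efficacy analyses, participants will be included in the analyses according to the planned investigational intervention". The same sentence continues that "for safety analyses, participants will be included in the analyses according to the investigational intervention they actually received".
- **What the trial assigns.** Section 2.1: "Participants in the ongoing MERINO trial are randomized to placebo or MTX for one year". For months 12 to 30, Table 2 in section 5 lists treatment as usual or "MTX 7,5-20mg weekly" after each MERINO arm, and 6.1.1 describes a standard course "and then 20 mg x 1 per week to end of study". Neither places any participant in a later group. Under 6.3 the treating physician decides together with the participant. MTX is usually tried for three months and then continued or stopped according to synovitis scores and self-reported effect.
- **Decision rule (9.3).** Superiority is concluded from the p-value for the difference between groups at study end, at the 5% level. The groups are not named there.

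**The concern.** The hypothesis and the grouping rule are both fixed in the protocol, and they point to different comparisons. Section 9.1 needs two of the four Table 2 sequences. Section 9.2 distributes all randomised participants by a *planned* intervention that is never defined beyond month 12.

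The 9.3 p-value carries the primary conclusion. If it comes from groups other than those in 9.1, rejecting the null would not support the claim about 30 months of MTX, and failing to reject would not speak against it. The comparison that does match 9.1 is not randomised, because continuing MTX depends partly on response (6.3). Its p-value alone therefore cannot demonstrate superiority, which is the aim stated in the synopsis.

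**Working it through.** The protocol derives no sample size, power or effect figure, so there is no number of its own to reproduce. The check is a comparison of passages, followed by an illustration of size.

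**Step 1: which groups can 9.2 produce?**

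| Reading of *planned* | Groups at month 30 | Same as 9.1? |
|---|---|---|
| MERINO allocation, the only treatment the trial assigns | Initial MTX vs initial placebo, later treatment mixed | No. Participants who went from MTX to treatment as usual, or from placebo to MTX, are counted inside the two groups |
| Treatment prescribed when MERINO ended | The four Table 2 sequences, as prescribed | Not as worded. Someone prescribed MTX at month 12 who stops at the three-month review has had 12 + 3 = 15 months, not 30 |
| Sequence actually received | The four Table 2 sequences, as taken | Closest to 9.1, but 9.2 keeps this basis for safety |

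The first reading suits the 12-month part of secondary objective 2. It does not give the 30-month contrast.

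**Step 2: does 6.3 repair this?** It says that length and dose of MTX will be adjusted for. That concerns covariates. It does not state who belongs to which group.

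**Step 3: size under the first reading (illustration only).**

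Inputs from the protocol: 153 participants; 12 months of MERINO plus 18 months of follow-up, 30 in total. Not given, and therefore assumed: 1:1 arms, all 153 followed, full adherence in the MERINO year, later treatment coded as MTX yes or no, and the same later duration d among MTX users in both arms. Let u_M and u_P be the later MTX uptake in the former MTX and placebo arms.

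- Difference in mean MTX exposure between MERINO arms: D = 12 + d(u_M − u_P) months, against 30 months in the 9.1 contrast.
- Share of participants on a 9.1 sequence: S = [u_M + (1 − u_P)]/2.

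| u_M | u_P | D (d = 18) | D/30 | S | S × 153 |
|---|---|---|---|---|---|
| equal | equal | 12 | 40% | 50% | 76.5 |
| 0.2 | 0.8 | 12 − 10.8 = 1.2 | 4% | 20% | 30.6 |
| 0.8 | 0.2 | 12 + 10.8 = 22.8 | 76% | 80% | 122.4 |
| 1 | 0 | 12 + 18 = 30 | 100% | 100% | 153 |

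With equal uptake, D = 12 for any d. The second and third rows are the extremes when each uptake lies between 0.2 and 0.8. The groupings coincide only in the last row, where every former MTX participant and no former placebo participant takes MTX later.

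**The case against.** The strongest reply is that 9.2 never mentions the MERINO arms. Section 6.3 speaks of four groups, Table 2 labels the sequences as study arms, and *planned* could mean what physician and participant agreed when MERINO ended. That reading yields the four sequences and still respects the distinction in 9.2 between planned and received. It stands as a possible reading. A reader might infer that 9.2 definitely compares the MERINO arms, or that the Table 2 groups can be formed only from treatment received. The document supports neither inference: the term is undefined, and prescription at month 12 is another basis for grouping. However, 9.2 does not state that basis, and it would still not give the 30 months of MTX that 9.1 names.

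A second reply is that the detail belongs in the SAP, as 9.3 says. The membership algorithm may well be there. But the contrast and the grouping basis are already fixed in the protocol. An SAP that follows 9.2 on its natural reading misses 9.1, and one that groups by treatment received departs from 9.2.

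A third reply is that analysing everyone randomised by allocation is good practice. That is accepted. The all-randomised set is not the fault; the mismatch with the stated hypothesis is.

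On size, the 40% and 50% follow directly from assuming equal uptake, and full follow-up is optimistic because attendance is voluntary (7.3). The figures show scale only, and months of exposure are not an effect size.

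**Conclusion.** The point holds as a mismatch between 9.1 and 9.2 that 9.3 carries into the primary conclusion. Under the natural reading, and also under the reading as prescribed, the study-end p-value does not test the 9.1 hypothesis as worded. This follows from the text and does not depend on the illustrative figures, which could lie anywhere in the stated ranges because the protocol gives neither arm sizes nor later uptake. It needs correcting in the protocol before analysis.

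**What to change.** Reconcile 9.1, 9.2 and 9.3 in one of two ways, and state which comparison is primary.

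**(a) Keep the 9.1 contrast.**
- Amend 9.2 so that the 30-month efficacy groups are the Table 2 sequences, with membership defined before analysis: either as prescribed at month 12, or as received according to the questionnaire and prescription database in 6.5. If as prescribed, word 9.1 as a comparison of prescribed sequences.
- Report MTX–MTX versus placebo–treatment as usual as a non-randomised comparison, and drop the wording that superiority is shown by the p-value alone.
- Handle confounding of the later treatment choice with data already collected. Ordinary adjustment for month-12 values can remove part of the first-year effect. One option is weighting for the month-12 choice, with pre-randomisation covariates in the outcome model.
- State that continuation depends on response (6.3), so groups by treatment received remain response-selected.
- Keep the MERINO-arm comparison for the 12-month analyses and as a named supportive analysis at month 30.

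**(b) Keep the 9.2 grouping.** Define *planned* as the MERINO allocation. Reword the 9.1 null and the synopsis aim to initial MTX versus initial placebo at month 30. Name the sequence comparison as a non-randomised secondary analysis.

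**Cost.** Either way this is a change of wording in a few places; the exposure sources (6.5) and the month-12 data (section 8) are already planned. Under (a), residual confounding may remain and the primary result no longer rests on all randomised participants. Under (b), the primary result no longer addresses 30 months of MTX, the question that 4.1 singles out. The choice is the sponsor's.

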9.3. Statistical Analyses

Continuous variables will be subject to linear mixed models. Binary response variables will be analyzed using logistic regression models (possibly adjusting for within-subject dependencies by mixed model approaches). Analyses at the joint level will apply generalized estimating equations (GEE) to account for dependency between joints within one person. The SAP will detail these procedures.

The hypotheses will be evaluated by the p-value associated with the between group difference at study end. A conclusion of superiority will be made if the null hypothesis is rejected on an overall significance level of 5%. The SAP will detail these procedures, as well as alternative and further supportive evaluations, such as analyses including unbalanced baseline predictors or modifications of the linear regression model in case validity assumptions are not met.

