6.3. Assignment to Study Intervention

The treating physician will decide, based on best clinical practice, if the patient should try MTX after the MERINO-trial. Central to this approach is the collaborative effort between the physician and participant, fostering an environment where patient perspectives are integral to treatment decisions. It will be emphasized by the physician prescribing MTX open-label that this is not evidence-based treatment until results of the MERINO-trial are published. We do, however, justify the continuation of MTX based on recent results from the METHODS trial (5). In the cases where the physician finds an indication for trying MTX after the MERINO trial, usual practice would be to try MTX for three months and then evaluate whether the patient should continue the treatment or not, based on synovitis scores and self-reported effects.

As described in section 5, this result in four groups in the MERINO:2 study, but since MTX treatment length and MTX doses could vary substantial in the observational time of the MERINO:2 study, we will adjust for this in the analyses.

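### Section 9.3 concludes superiority from groups formed by treatment choice after month 12, and Section 9.2 leaves the grouping for that contrast undefined

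*Protocol*

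**What the plan says.** Section 9.1 states the primary null hypothesis as "MTX treatment for 30 months is not different from placebo (12 months) and subsequent treatment as usual (18 months"), with respect to Verbruggen-Veys progression. Secondary outcomes (1) use the same contrast for the KL scale and the OARSI atlas. These are two of the four sequences listed under Study Arms and Duration in the synopsis.

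Section 6.3 describes how the sequences arise: "The treating physician will decide, based on best clinical practice, if the patient should try MTX after the MERINO-trial". Usual practice is then a three-month trial of MTX, and the physician will "then evaluate whether the patient should continue the treatment or not, based on synovitis scores and self-reported effects". The same section adds: "MTX treatment length and MTX doses could vary substantial in the observational time of the MERINO:2 study, we will adjust for this".

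The synopsis calls the study open-label and observational, with main objectives that are exploratory. The synopsis and Section 9.1 nevertheless set out to demonstrate superiority. Section 4.1 presents the comparison of the two extreme sequences as showing what long-term MTX does. Section 9.3 fixes the rule: "A conclusion of superiority will be made if the null hypothesis is rejected on an overall significance level of 5" per cent. Baseline covariates appear there only among "alternative and further supportive evaluations, such as analyses including unbalanced baseline predictors", which the SAP is to detail.

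On populations, Section 9.2 defines the full analysis set as everyone randomised. It says "The full analysis set will be used to analyze endpoints related to the efficacy objectives" and that for efficacy "participants will be included in the analyses according to the planned investigational intervention".

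**The concern.** Two problems meet in the primary analysis.

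First, membership of the two compared groups depends on a decision taken after randomisation, on grounds (synovitis, perceived effect, wish for treatment) that may predict progression. A difference between such groups can come from the drug, from the choice, or from both. A p-value below 0.05 cannot tell these apart, yet the protocol turns it into a superiority conclusion. The adjustments that the protocol names do not address the reasons for choosing MTX. Length and dose describe exposure, and covariates picked because they look unbalanced are offered only as an example of supportive work.

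Second, MERINO:2 randomises nobody and assigns no treatment after month 12. Grouping by planned intervention therefore has no defined meaning for the Section 9.1 contrast. The only assignment ever planned is the MERINO arm, and grouping by that arm answers a different question. Two analysts following the same protocol could report different primary results from the same data.

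**Working it through.** The protocol gives no figure to reproduce here: it states no power, effect size or expected MTX uptake, and Section 9.5 says the sample size has no statistical basis.

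**Inputs from the protocol.** 153 candidates; 12 months of MERINO plus 18 months of follow-up, 30 in all; four sequences; 5% level.

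**Assumptions, not in the protocol.** Allocation 77 (MTX) and 76 (placebo); MTX uptake after month 12 of 20–50% per arm; 75% attendance at random.

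**1. Who is in the Section 9.1 contrast.** With equal uptake u, the share is (77u + 76(1 − u))/153.
- u = 20%: (15.4 + 60.8)/153 = 49.8%
- u = 35%: (26.95 + 49.4)/153 = 49.9%
- u = 50%: (38.5 + 38)/153 = 50.0%

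So about half of those who attend are in the contrast at any equal uptake. At 75% attendance (about 115 people) this is roughly 12 v 46, 20 v 37 and 29 v 28. With unequal uptake the share moves: (38.5 + 60.8)/153 = 65% at 50% in the MTX arm and 20% in the placebo arm, and (15.4 + 38)/153 = 35% the other way round.

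**2. What grouping by MERINO arm compares.** The nominal difference in MTX exposure is 12 + 18 × (uptake in the MTX arm − uptake in the placebo arm) months.
- Equal uptake: 12 + 0 = 12
- Difference +0.3: 12 + 5.4 = 17.4
- Difference −0.3: 12 − 5.4 = 6.6

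It reaches 30 only if every former MTX participant continues and no former placebo participant starts. The formula assumes full adherence in year one and all-or-nothing use afterwards.

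**3. How selection moves the error rate.** If choice shifts the two groups apart by d standard deviations with no drug effect, two-sided rejection is P(|Z + d/√(1/n₁ + 1/n₀)| > 1.96). With 38 v 38 (50% uptake, everyone attending) and an assumed d = 0.3: √(2/38) = 0.229; 0.3/0.229 = 1.31; P(Z > 0.65) + P(Z < −3.27) ≈ 26%. With d = 0 it is 5%.

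**4. Illustration by mechanism.** 10,000 simulated studies per scenario, no drug effect, 75% attendance, log-odds 1 per SD for choosing MTX, group-only t-test of the Section 9.1 contrast. Entries are two-sided rejection in % (in brackets, the part favouring MTX) at equal uptake of 20/35/50%. The correlation is between the selection state and progression.

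| Choice of MTX | Correlation 0.3 | Correlation 0.5 |
|---|---|---|
| Need-based in both arms | 11.8/14.4/15.6 (0.3/0.2/0.2) | 25.2/32.6/35.7 (0.1/0.1/0.0) |
| Response-based continuation in the MTX arm | 9.6/8.9/8.0 (9.0/8.3/7.1) | 17.5/16.2/12.1 (17.3/16.1/11.8) |
| Response in the MTX arm, need in the placebo arm | 7.9/5.9/5.1 (7.1/4.3/2.6) | 12.1/7.6/5.1 (11.8/6.9/2.5) |

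At correlation 0.1 rejection is 4.6–6.1%. Without selection it is 4.8–5.2%. The randomised-arm comparison stays at 4.6–5.6%.

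**5. What adjustment can do.** Within-arm weights on three month-12 covariates (3,000 runs) gave 3.6–5.5% at 35–50% uptake when month-12 data capture the choice, but 7.2–8.8% at 20% uptake (6.1% there without selection). When the choice follows a later state correlated 0.6 with month 12, rejection was 9.1–18.3% (need), 5.1–11.6% (response) and 4.1–10.7% (opposing). The SD of the estimate rose by 5–33%.

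**The case against.** The strongest reply is that the protocol is open about being observational and that Section 9.3 leaves the details to a SAP not at hand. Its examples of supportive analyses are not a closed list, so a reader who infers that the main model will be unadjusted goes beyond the text. That stands, and the choice of covariates and method is not part of this point. It does not reach the superiority rule, the stated aim or the grouping, all of which the protocol fixes itself.

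The simulation is also open to challenge. Selection strength, uptake, attendance and correlation are all assumed, and the test is simpler than the mixed models and GEE named in Section 9.3. In a joint-level GEE-type check, rejection was already 5.6–7.1% with no selection, so part of any excess there is small-sample error in the robust standard errors. The figures show only that the nominal level is not assured.

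Four stronger readings are tempting but not supported:
- *The other two sequences have no place in Section 9.1.* This holds for the primary hypothesis and Secondary (1). Secondary objective (2) compares MTX with placebo/treatment as usual without requiring 30 months of MTX, and Section 4.1 gives the placebo→MTX group a purpose.
- *All 153 will be analysed.* That number counts candidates. Consent is separate, attendance is voluntary, and Section 7.3 rules out imputation for loss to follow-up.
- *Section 9.2 makes the contrast impossible to estimate.* The synopsis and Table 2 treat the sequences as arms, and a four-group model on the whole set could estimate the contrast. The defect is that the grouping is undefined, with one natural reading that contradicts Section 9.1.
- *The bias will favour MTX.* Section 2.1 describes off-label use for unmanageable pain and inflammation, which suggests need-based choice; Section 6.3 supports response-based continuation. These push in opposite directions.

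**Conclusion.** The point holds on the text. For the primary hypothesis and Secondary (1), a conclusion of superiority at 5% is stronger than a contrast formed by choice after month 12 can support, if that choice is related to progression. The adjustments named in the protocol do not deal with the reasons for that choice, though the SAP may add others. Separately, Section 9.2 does not define the groups for this contrast. Read as the MERINO arms, it pools all four sequences and compares groups nominally 12 months of MTX apart at equal uptake instead of 30.

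The size of the bias cannot be derived from the documents. On the assumptions shown, two-sided rejection with no drug effect runs from about 5% (weak selection, or opposing selection at 50% uptake) to 36% (strong need-based selection, nearly all against MTX). Response-based continuation gives about 8–17%, nearly all favouring MTX. The share of attenders in the contrast, about half, rests on near-equal allocation and equal uptake.

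**What to change.** 1. **Claim.** In the synopsis and Sections 4.1, 9.1 and 9.3, replace the aim to demonstrate superiority, the statement that the comparison reflects the effect of MTX, and the superiority conclusion. For this contrast, state an estimated association with its confidence interval.
2. **Groups.** In Section 9.2, define the analysis set as consenting participants with 30-month data. Define the four sequences by treatment actually received after month 12, including who counts as MTX→MTX. Name MTX→MTX versus placebo→treatment as usual as the primary contrast, say where the other two groups are reported, and report the randomised MERINO-arm comparison beside it.
3. **Adjustment.** In Section 9.3, state only that the main analysis of this contrast adjusts for prespecified predictors of the post-month-12 choice, not for those found unbalanced. Covariates and method can stay in the SAP. First state whether progression runs from MERINO entry or from month 12: Section 8 takes month-12 data as baseline, while Section 9.1 speaks of 30 months of treatment. The 18-month and 30-month labels denote the same visit; only the starting point is open. It matters because adjusting for month-12 variables can remove part of a first-year effect.

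The cost is protocol wording, with no new visits or data. The price is a weaker claim and wider intervals. At 20% uptake (about 12 on MTX→MTX) only a few covariates are usable, and participants who left MERINO early may lack month-12 data. Adjustment reduces confounding but may not remove it, in particular from the three-month continuation decision, for which the Schedule of Activities plans no synovitis or questionnaire data. Items 1 and 2 therefore carry most of the benefit.

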9.5. Sample Size Determination

The sample size is not based on statistical considerations. All participants entering the MERINO trial will be asked to complete a 30-month follow-up visit in the MERINO:2 study. The MERINO trial aims to include 153 participants.

10. Supporting Documentation and Operational Considerations

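### Section 9.3 gives baseline predictors no stated role except in supportive analyses, and there only if unbalanced by an undefined check, although the main contrast is not randomised after month 12

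*Protocol*

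**What the plan says.** Section 9.3 sets the decision rule: "The hypotheses will be evaluated by the p-value associated with the between group difference at study end". On the model it says "Continuous variables will be subject to linear mixed models", with logistic regression for binary outcomes and GEE at joint level. No covariate is named for any of these models.

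Baseline predictors appear once, among the items left to the SAP: "alternative and further supportive evaluations, such as analyses including unbalanced baseline predictors or modifications of the linear regression model". No test, threshold or variable list defines unbalanced.

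Other sections bear on this:

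- Section 9.1 compares MTX for the whole 30 months with placebo followed by treatment as usual.
- Section 6.3 says how treatment is set after the first year: "The treating physician will decide, based on best clinical practice, if the patient should try MTX after the MERINO-trial". It adds that continuation is judged after about three months on synovitis scores and self-reported effect. It also promises adjustment for MTX dose and duration.
- Section 2.1 gives unmanageable pain and inflammation as the usual reason for off-label MTX.
- Section 9.5 gives the ceiling on numbers: "The MERINO trial aims to include 153 participants". No power calculation is made.
- Section 8 takes the 12-month MERINO data as the MERINO:2 baseline.

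**The concern.** In a fully randomised comparison, loose wording about unbalanced predictors would cost mostly precision. Here the second 18 months of treatment are chosen. The protocol names pain and synovitis as reasons for the choice, so both may differ systematically between the groups compared, yet neither has a stated place in the main comparison. The dose and duration adjustment in 6.3 concerns exposure after baseline and does not address this.

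Observed imbalance is the wrong criterion for entry. In small groups a real difference in a confounder often passes as balanced. A strong predictor of the outcome belongs in the model even when it is balanced, because it reduces residual variance. With no check defined, the covariate set could also be settled after the data are seen. At stake are residual confounding in the headline estimate and precision given away in a study capped at 153 people.

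**Working it through.** The protocol states no power, effect size or SD, so there is no figure of its own to reproduce. The size of the problem has to be shown under assumptions.

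**Inputs**

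- From the protocol: at most 153 participants (9.5), four groups (section 5), 5% significance level (9.3), two-sided hypotheses (9.1), voluntary follow-up without imputation (7.3).
- Assumed: equal groups with full participation, 153/4 ≈ 38 each; 27 each for 70% participation (0.7 × 38 ≈ 27); 20 each as a low case. The balance check is a two-sided 5% test. There is one normally distributed baseline covariate with correlation r = 0.5 to the outcome, and no true MTX effect. SMD is the true group difference in the covariate, in SD units.

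**Step 1. Chance that the check flags a true difference**

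Normal approximation: P ≈ Φ(SMD × √(n/2) − 1.96).

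- n = 38: √(38/2) = 4.36. At SMD 0.3, 0.3 × 4.36 − 1.96 = −0.65, so P ≈ 26%. At SMD 0.5, 2.18 − 1.96 = 0.22, so P ≈ 59%.

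| n per group | SMD 0.2 | 0.3 | 0.4 | 0.5 | 0.8 | SMD flagged half the time |
|---|---|---|---|---|---|---|
| 38 | 14% | 26% | 41% | 59% | 94% | 1.96/4.36 = 0.45 |
| 27 | 11% | 20% | 31% | 45% | 84% | 0.53 |
| 20 | 9% | 16% | 24% | 35% | 72% | 0.62 |

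**Step 2. Bias and type I error, n = 38, r = 0.5**

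Unadjusted bias = r × SMD. At SMD 0.3 this is 0.5 × 0.3 = 0.15 SD. The standard error is √(2/38) = 0.229, so the test statistic is shifted by 0.15/0.229 = 0.65. The chance of exceeding ±1.96 is Φ(−1.31) + Φ(−2.61) ≈ 0.10.

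Simulation with 20,000 data sets per setting gives:

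| SMD | Unadjusted: bias, type I error | Adjusted only if flagged: bias | Always adjusted: bias |
|---|---|---|---|
| 0.2 | 0.10 SD, 7.0% | 0.06 SD | about 0 |
| 0.3 | 0.15 SD, 9.9% | 0.08 SD | about 0 |
| 0.5 | 0.25 SD, 18.7% | 0.06 SD | about 0 |

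Over these three rows, type I error for adjusting only if flagged is 4.9–6.0%. Always adjusting keeps it at about 5%.

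At SMD 0.3, adjusting only if flagged removes about half the bias although it flags only a quarter of data sets. The flagged data sets are those with the largest observed imbalance.

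**Step 3. Precision with no imbalance**

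A covariate with r = 0.5 leaves a residual variance fraction of 1 − 0.5² = 0.75. For a true effect of 0.5 SD, simulated power rises from 58% to 70% at n = 38 and from 44% to 54% at n = 27. The gain depends on r: at n = 38, adjusted power is 61% for r = 0.3 and 85% for r = 0.7.

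**The case against.** The strongest reply is that 9.3 fixes very little. Its wording is illustrative, and it hands the detail over: "The SAP will detail these procedures, as well as alternative and further supportive evaluations". Covariates of the main models are neither listed nor excluded, and such lists commonly sit in the SAP, which is not at hand. Because the primary outcome is progression, the starting radiograph already enters it, and a mixed model could carry the baseline value as a covariate or a repeated measure. This stands. A reader might infer that the main comparison ignores baseline values or that 9.3 forbids them there; the text does not support that.

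A reader might also infer that the check would miss most confounders. No check is defined. Even a 5% test would catch 94% of 0.8 SD differences at 38 per group, and it misses more often than not only below about 0.45 SD at that size. The error rate near 10% belongs to a wholly unadjusted analysis. For adjusting only if flagged, the inflation from one covariate is slight.

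Two further limits stand. Section 9.2 places all randomised participants by planned intervention for efficacy, which conflicts with the treatment-received contrast in 9.1. If 9.2 governs, randomisation covers baseline confounding, and adjustment serves mainly precision and selective follow-up. Also, values from before randomisation cannot remove selection on month-12 status or on response during the three-month trial of MTX.

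None of this makes imbalance a sound criterion for entry. Leaving detail to the SAP does not help if the SAP follows the one rule that the protocol states.

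**Conclusion.** The point holds as a poor stated rule, not as proof that the main analysis will be unadjusted. The only role 9.3 gives baseline predictors is supportive and conditional on an undefined imbalance, for a contrast whose second period is chosen partly on pain and synovitis.

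At 38 per group, r = 0.5 and a 0.3 SD imbalance, bias is 0.15 SD if the main comparison is unadjusted, about 0.08 SD under adjustment only if flagged, and about 0 under fixed adjustment. Without imbalance, fixed adjustment raises power from 58% to 70% for a 0.5 SD effect. Group sizes, r, the imbalance and the form of the check are all assumptions. The near-zero bias under fixed adjustment holds for confounding captured by the measured baseline variable, and does not make the treatment-received contrast equivalent to a randomised one. The change should be made because it is cheap and improves both bias and precision.

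**What to change.** In 9.3, delete the unbalanced condition. State that the primary and secondary models include a short fixed set of MERINO-entry (pre-randomisation) values whatever their observed balance:

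- the baseline value of the outcome (in joint-level models, the joint's own baseline phase);
- baseline pain;
- baseline synovitis.

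Age, sex and BMI may be added, but the documents do not establish them as predictors of Verbruggen-Veys progression. Report the unadjusted result as supportive.

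For the 30-month contrast, do not enter the month-12 values that section 8 calls baseline as simple covariates. They follow the first randomised year, and adjusting for them could remove part of the effect being estimated. State that selection on month-12 status and later response remains, so the treatment-received contrast stays observational. Reconcile 9.1 with 9.2 on which groups are compared, since that decides whether the gain is mainly in bias or in precision.

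The cost is a few sentences in 9.3, matching text in the SAP and a few degrees of freedom. No new data are needed: the schedule of activities already has hand radiographs and finger ultrasound at MERINO screening, and hand pain at screening and month 0.
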